The Role of Pre-deployment Retraction in Decreasing Biopsy
Clip Migration During Stereotactic Breast Biopsies

Study Protocol & Statistical Analysis Plan

NCT04398537

Date of Last Protocol Approval- 05-Apr-2023

[name], D.O., Associate Program Director, Diagnostic
Radiology Residency Program
Associate Professor, Breast Imaging Section, Principal
Investigator
University of Alabama at Birmingham
[name]

Evaluating the position of a breast biopsy clip introducer and whether or not retraction prior to deployment results in less clip migration

Principal Investigator: [name], DO
Assistant Program Director, Radiology Residency Program
Assistant Professor
Breast Imaging Section
UAB Department of Radiology
[name]
[name]
[contact]
Email: [contact]

Original Protocol: 4/09/2020

1. STUDY DESIGN / SUMMARY:

This will be a single-center prospective randomized control trial that IRB-approved study. We plan to enroll 250 female patients presenting to UAB for stereotactic biopsy. This study is a prospective will target approximately 250 patients. This will be a HIPPA-compliant randomized control trial planned on spanning approximately six months' time. Patients will be entered into the study only based on their already scheduled stereotactic biopsy procedure. Patients will be informed of the study and they will be offered the opportunity to participate or not participate in the study. Their participation is completely voluntary. This study will not involve any intervention that is not already a part of standard care. Patients will be randomized to two groups, one group that will undergo clip placement with approximately with a 5 mm retraction of the biopsy clip post-placement and one that will involve no retraction prior to deployment.

2. BACKGROUND AND RATIONALE

Clip placement after stereotactic biopsy in breast imaging procedures has been an important part of breast imaging for years. There have been numerous studies documenting clip migration, and it is now a well-known phenomenon. Numerous case reports describe varying locations of clips following biopsy, some being as much as 5 cm from the biopsy site. This creates a problem in both benign and malignant diagnoses. In the setting of a benign biopsy, a clip remains important to provide correlation with a biopsy finding and the original suspicious mammographic site. In malignant diagnoses, the implication is more significant as the clip provides the localization site for excision. Clip migration has been suspected as the cause of up to 60% margin positivity (vs 0% when localizing the biopsy site by using hematoma identification) in breast cancer cases.¹ Although there have been recommended methods of deployment, vacuuming of cavity, release of compression after biopsy, and first post-biopsy mammography positioning techniques, there has been no prospective study assessing technique of clip retraction prior to deployment. Our hypothesis is that retracting to clip 5 mm before clip deployment will help to decrease clip migration. This will help improved accuracy of biopsy site localization and in cases of malignancy, will allow for less complicated, better localized, and improved results of tumor targeting for surgical resection.

3. OBJECTIVES

3.1 Primary Objective

To determine which method decreases clip migration better, retracting the clip deployment apparatus 5 mm before deployment or not retracting.

3.2 Secondary Objectives

- 3.2.1** Compare different breast densities (entirely fatty, scattered fibroglandular densities, heterogeneously dense, extremely dense) and their impact on clip migration in both groups (retracted vs nonretracted).
- 3.2.2** Compare different approaches (lateral, medial, superior) to biopsy and evaluate if they have an impact on clip migration in both groups (retracted vs nonretracted).
- 3.2.3** Evaluate if thinner or thicker breasts result in more or less clip migration in both groups (retracted vs nonretracted).
- 3.2.4** Evaluate if patient's age correlates with more or less clip migration in both groups (retracted vs nonretracted).

4. PARTICIPANT SELECTION

This will be a single-center randomized control prospective IRB-approved study. We will enroll 250 female patients presenting to have stereotactic breast biopsy procedures. We will approach all stereotactic biopsy patients (less excluded patients), targeting 300 with the goal of 250 by 1 year.

4.1 Inclusion Criteria

All 18-99 year-old healthy females with recommendation for stereotactic biopsy.

4.2 Exclusion Criteria

- 4.2.1** If there is no clip present on post-clip mammography, the patient will be excluded from the trial (even if a clip was replaced).
- 4.2.2** If 2 clips were placed (due to one not being seen initially), the patient will be excluded.
- 4.2.3** Patients who have undergone reduction mammoplasty will also be excluded as this has been discussed as a potential reason for clip migration⁸.
- 4.2.4** No pregnant females will be included. There will be no males included.
- 4.2.5** There will be no mentally impaired patients included.
- 4.2.6** No non-english speaking patients included in the study.
- 4.2.7** There will be no prisoners included in this study.
- 4.2.8** Inability to provide written informed consent
- 4.2.9** Males will not be included.
- 4.3** Inclusion of all races and ethnic groups are eligible for this trial. There is no bias towards age or race in this trial.

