3. ATEC machine is placed on biopsy setting until visualization of x-rayed specimens
4. When samples are determined to be adequately retrieved, the clip will be placed (the same clip will be chosen for all procedures to improve standardization unless the attending radiologist determines another clip would be needed).
5. Biopsy clip is then advanced to the site.

At this point, everything performed will be routine.

Study protocol:

Arm 1: Advancing the clip to the biopsy site and deploying.

Arm 2: Advancing the clip to the biopsy site and retracting 5 mm and then deploying.

Standard protocol

After imaging is obtained to ensure that the clip is visualized, the introducer and clip are removed together.

Patient is then slowly released from mammographic compression maintaining pressure on the breast for at least five minutes. Slow release of pressure is performed.

The patient is then informed of post-biopsy changes. Pressure is held until hemostasis is achieved and a sterile skin glue is applied to the skin incision at the entrance site of the biopsy needle.

A two-view mammogram is performed with the first image obtained in the same position as the biopsy is performed.

Clip migration will be measured on the post-biopsy mammogram compared to the pre-biopsy mammography exam. Clip migration will be measured by the location of the clip with respect to the biopsy site on the immediate post-clip mammography images. While delayed clip migration has been found in case reports, the number of cases of this phenomenon is not felt to warrant additional mammography exams for this study.⁸ The millimeters of clip migration will be measured on the CC view and on the true lateral (ML or LM) views. Although migration usually only occurs in one plane, both planes will be reviewed and if there is migration in two planes, one component factor (Pythagorean Theorem as has been used on prior studies¹) will be calculated.

We will consider significant migration is anything greater than 10 mm from the biopsy site. The use of 10 mm has been documented on prior studies and will be considered as a differentiation point in this study between significant and nonsignificant movement. A further reason for the use of the 10 mm cut off is that at this institution, Savi Scout devices are commonly used for localization. This device is 12 mm long and can accurately be placed at a location bridging the biopsy site and biopsy clip. Any complications will be reported.

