12.1 Sample size justification

A total of 250 female patients presenting to UAB for stereotactic biopsy will be randomly assigned as 1:1 ratio to Arm1 (n=125) with advancing the clip to the biopsy site and deploying, or Arm2 (n=125) with advancing the clip to the biopsy site and retracting 5 mm and then deploying. Our hypothesis is that retracting to clip 5 mm before clip deployment will decrease clip migration, e.g. only 20% or less of breast biopsy patients who will have significant migration (greater than 10 mm from the biopsy site) while advancing the clip to the biopsy site and deploying without retracting will have at least of 50% significant migration. This size of 125 in each arm will have 99.9% power to test 30% difference (20% vs 50%) or >90% power to test at least 20% difference in proportion of patients who will have significant migration using one-sided Fisher's Exact test at 5% significant level (Table 1).

Table 1 Statistical Power to Test Differences Between Two arms.

Significant migration in Arm1 (%)	Significant migration in Arm2 (%)	Type I error (%)	Power (%)
50	15	5	100
50	20	5	99.9
50	25	5	99.1
50	30	5	93.1
50	15	1	100
50	20	1	99.6
50	25	1	95.4
50	30	1	78.5

A sample size of 125 will also produce two-sided 95% confidence interval to estimate the mean distance of migration with 0.177 standard deviation to the limits for each arm. Patients enrollment is expected to be completed within one year.

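### Exclusions 4.2.1 and 4.2.2 act after the assigned deployment technique has been used, so the primary comparison could be biased in either direction and the plan would not show it

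*Combined protocol and SAP*

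**What the plan says.** Section 4.2 (Exclusion Criteria) opens with two items that concern the clip itself. Item 4.2.1: "If there is no clip present on post-clip mammography, the patient will be excluded from the trial (even if a clip was replaced". Item 4.2.2: "If 2 clips were placed (due to one not being seen initially), the patient will be excluded". The remaining items, 4.2.3 to 4.2.9, can be judged before the procedure and are not in question.

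Section 6 sets the order of events. The steps are routine until the clip reaches the site. The arms then part: Arm 1 deploys at once, and the other arm is described as "Arm 2: Advancing the clip to the biopsy site and retracting 5 mm and then deploying". Visibility is checked afterwards: "After imaging is obtained to ensure that the clip is visualized, the introducer and clip are removed together". A two-view mammogram follows, and migration is measured on it.

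Section 12.1 states: "A total of 250 female patients presenting to UAB for stereotactic biopsy will be randomly assigned as 1:1 ratio to Arm1 (n=125", with the same number in Arm 2. The documents do not say when randomisation takes place. Section 13.2 compares the proportions with migration beyond 10 mm by Fisher's exact test. Neither section names an analysis population, a rule for absent or second clips, a count of them by arm, or a sensitivity analysis.

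**The concern.** Items 4.2.1 and 4.2.2 are written as eligibility criteria, but nobody can apply them at entry. Whenever randomisation occurs, the arm must be known before deployment, and both rules act after it. The mammogram that decides 4.2.1 is also the one that supplies the outcome.

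Removing patients on something that may result from the technique under test gives up the protection of randomisation. Unequal counts alone do no harm. Bias needs the exclusions to differ between arms in number or type, and the excluded patients' outcomes to differ from those of the patients retained. If more patients are removed from the retraction arm and their clips would have been beyond 10 mm, retraction looks better than it is; if their clips would have stayed in place, a real benefit is hidden. The plan as written gives the reader no means of telling these cases apart.

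**Working it through.** **Inputs from the documents.** 125 per arm; one-sided Fisher's exact test at 5%; expected rates of at least 50% in Arm 1 and 20% or less in Arm 2; Table 1 also has a 50% v 30% row (section 12.1).

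**The plan's own figures.** Exact power at 125 per arm is 99.96% for 50% v 20% (Table 1: 99.9%) and 93.5% for 50% v 30% (Table 1: 93.1%). The stated power reproduces and is not in dispute. Loss of numbers alone matters little: with 113 per arm, power for 50% v 30% is 90.3%.

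**Assumptions.** The documents give no loss rate and no outcomes for lost patients. I take losses of 2%, 5% and 8%, and three cases for the lost clips: all beyond 10 mm (failures), none beyond 10 mm (non-migrators), or like the retained ones.

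**Shift in one arm's observed rate.** With true rate F and loss l, the analysed rate is (F − l)/(1 − l) if the lost are failures, F/(1 − l) if they are non-migrators, and F if they are like the rest. For example, F = 50% and l = 5% give 0.45/0.95 = 47.4% or 0.50/0.95 = 52.6%.

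| Loss | Shift at F = 50% | Shift at F = 20% |
|---|---|---|
| 2% | −1.0 to +1.0 points | −1.6 to +0.4 |
| 5% | −2.6 to +2.6 | −4.2 to +1.1 |
| 8% | −4.3 to +4.3 | −7.0 to +1.7 |

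**False finding of benefit for retraction.** True rates are equal in the two arms; one-sided Fisher at 5%; n = 125 × (1 − l), rounded. The 50% rate is the plan's Arm 1 figure; a 20% rate in Arm 1 is below what the plan expects. With no exclusions the rate is 4.4% (F = 50%) or 3.7% (F = 20%). Cells show F = 50% / F = 20%.

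| Loss, Arm 1 v Arm 2 | Lost are failures | Lost are non-migrators | Lost like retained |
|---|---|---|---|
| 0% v 2% | 5.2% / 7.1% | 2.6% / 3.1% | 3.7% / 3.6% |
| 0% v 5% | 9.0% / 17.1% | 1.5% / 2.3% | 4.0% / 3.6% |
| 0% v 8% | 13.7% / 35.5% | 0.7% / 1.6% | 3.9% / 3.5% |
| 5% v 0% | 1.5% / 0.4% | 9.0% / 5.4% | 4.0% / 3.5% |
| 8% v 0% | 0.7% / 0.06% | 13.7% / 6.9% | 3.9% / 3.5% |

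**Equal counts do not rule bias out.** As an extreme bound, let Arm 1 lose only non-migrators and Arm 2 only failures. The false-benefit rate is 7.9% / 8.1% at 2% loss in each arm and 17.4% / 22.3% at 5%. With the types swapped it is 2.0% / 1.4% and 0.5% / 0.2%.

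**Two-sided test.** Section 13.2 does not state sidedness. With a two-sided 5% test, counting rejections in favour of retraction, the rate at 0% v 8% with failures lost is 8.3% / 27.8%, against 1.8% / 1.7% with no exclusions.

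**Power.** For a true 50% v 30%, power runs from 77.2% to 98.1% at 8% v 0%, and from 83.7% to 99.4% at 0% v 8%. For 50% v 20% it stays at 99.48% or more under one-arm losses up to 8%.

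**Hypothetical example, ten patients excluded from Arm 2.**

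| Analysis | Arm 1 v Arm 2 | One-sided p | Two-sided p |
|---|---|---|---|
| Ten excluded | 50/125 v 32/115 | 0.032 | 0.057 |
| Ten counted as failures | 50/125 v 42/125 | 0.179 | 0.359 |
| Ten counted as non-failures | 50/125 v 32/125 | 0.011 | 0.022 |

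**The case against.** The strongest reply is that the harm is conditional on facts that the documents do not supply: a material rate of absent or second clips, a difference between arms, and different outcomes among those lost. There is no evidence that retraction affects clip visibility. That stands, and it is why the claim is that the comparison could be biased, not that it is.

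The largest figures are also corner cases. The 35.5% needs a 20% rate in both arms, no loss in Arm 1, 8% loss in Arm 2 and every lost clip a migrator, which removes 8 of the 20 points of migration in Arm 2 and none in Arm 1. At the 50% rate, imbalances of one or two points leave the false-benefit rate at 5.2% or below. These figures are bounds and should be read as such.

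A further point is that an absent clip has no distance. With two clips, the first may not be identifiable, because "the same clip will be chosen for all procedures to improve standardization unless the attending radiologist determines another clip would be needed". Counting an unseen clip as a failure also moves the question away from the primary objective, "To determine which method decreases clip migration better, retracting the clip deployment apparatus 5 mm before deployment or not retracting". Both points stand, and they limit the remedy. They do not justify taking these patients out of the trial without a count by arm or a bound.

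Finally, section 4 says "We will approach all stereotactic biopsy patients (less excluded patients), targeting 300 with the goal of 250 by 1 year". This may refer only to the baseline criteria, and the margin between 300 and 250 might be read as an allowance for such losses, though the text does not say so. Nothing here depends on how that sentence is read.

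**Conclusion.** The concern holds and should be fixed. The order of steps in section 6 is enough to establish that 4.2.1 and 4.2.2 remove patients on what is seen after the assigned technique, and nothing in sections 12.1 or 13.2 repairs or reveals the effect.

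Neither the direction nor the size can be fixed from the documents. If exclusions are rare, or the excluded resemble the retained, the effect is negligible. With a one-arm loss of 5% at a 50% rate, the false-benefit rate lies between 1.5% and 9.0%, against 4.4% with no exclusions. If migration is less common than the plan expects, the upper bound rises faster. At the plan's own 50% v 20% the conclusion would survive one-arm losses up to 8%; at 50% v 30% power could fall to 77.2%. The problem is possible bias, not the number of patients lost.

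**What to change.** - Take 4.2.1 and 4.2.2 out of the exclusion criteria, and state when randomisation happens.
- State in section 13.2 that every randomised patient is kept and analysed in the assigned arm.
- Report absent-clip and second-clip events by arm, with a between-arm comparison.
- Pre-specify how these patients count in the binary analysis. Counting them as failure to mark the site is one option, either as the primary rule or as a key sensitivity analysis that leaves the 10 mm endpoint unchanged.
- Give the complete-case result together with best-case and worst-case bounds.
- Use the first clip's distance only where that clip can be identified. Restrict the distance analysis to measurable clips and label it as subject to the same selection.

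The cost is protocol and SAP wording and a little more analysis; no extra patients or images are needed. If the composite were made primary, the endpoint would be somewhat broader than the migration objective in section 3.1 and the 50% and 20% assumptions in section 12.1. Keeping migration beyond 10 mm as primary, with the composite as a sensitivity analysis, avoids that.

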5. RECRUITMENT AND SCREENING

5.1 Recruitment Process

Patients will be presenting to the The Kirklin Clinic at The University of Alabama at Birmingham, Fifth floor Mammography for the purpose of previously recommended stereotactic biopsy. The study coordinator, PI, or participating attending radiologist will arrange the interview and provide all data for entry in a secure web-based research database.

5.2 Screening Process

The study coordinator, PI, or participating attending radiologist will screen potentially eligible patients.

6. PROTOCOL PROCEDURES, METHODS, AND DURATION (LAYMAN'S DESCRIPTION)

After confirmation of patient eligibility, the study coordinator, PI, or participating attending radiologist will obtain written informed consent. The informed consent process may take up to 10 minutes. The patients will be discharged from the study after data has been recorded.

Standard of Care:

The stereotactic biopsy will proceed as normally scheduled. This procedure involves the patient presenting to the fifth floor of The Kirklin Clinic (TKC) at The University of Alabama at Birmingham. Once she checks in, she is escorted to a changing room where she changes into a gown. She is then brought back to the biopsy suite by the technologist. The technologist reviews the biopsy procedure with the patient. The attending radiologist then is notified and joins the technologist and patient in the biopsy suite. The radiologist reviews the biopsy with the patient and obtains informed consent.

Study protocol:

After informed consent for the procedure, the radiologist will discuss the study with the patient after the patient. The patient will have time to ask questions and the radiologist will provide answers. If the patient expresses understanding and agrees to participate in the study, consent will be obtained in written form on a document separate from her biopsy consent document. This will be placed in a secure location and locked in a cabinet in the mammography department on the fifth floor TKC, accessible only to the PI.

Standard of Care:

The procedure will take place as normally planned with the patient being positioned in craniocaudal (CC), lateral-medial (LM), or medial-lateral (ML) position determined by the radiologist ahead of time. The choice of positioning is decided on by the radiologist based on experience and best pathway to obtain to target. Images are obtained to verify the target location. The skin is cleaned and skin/breast anesthetized. A needle (9 gauge 10 cm Eviva vacuum-assisted needle attached to an ATEC vacuum suction machine) is placed to obtain the sample of the biopsy target. The tissue undergoes x-ray imaging to ensure adequate sampling of tissue. Once sampling is considered appropriate, standard steps are performed in the following manner:

1. After biopsy, the cavity is flushed with sterile saline.
2. Tubing is disconnected to allow for suction of fluid from the biopsy cavity. Samples are retrieved from the collection chamber.
3. ATEC machine is placed on biopsy setting until visualization of x-rayed specimens
4. When samples are determined to be adequately retrieved, the clip will be placed (the same clip will be chosen for all procedures to improve standardization unless the attending radiologist determines another clip would be needed).
5. Biopsy clip is then advanced to the site.

At this point, everything performed will be routine.

Study protocol:

Arm 1: Advancing the clip to the biopsy site and deploying.

Arm 2: Advancing the clip to the biopsy site and retracting 5 mm and then deploying.

Standard protocol

After imaging is obtained to ensure that the clip is visualized, the introducer and clip are removed together.

Patient is then slowly released from mammographic compression maintaining pressure on the breast for at least five minutes. Slow release of pressure is performed.

The patient is then informed of post-biopsy changes. Pressure is held until hemostasis is achieved and a sterile skin glue is applied to the skin incision at the entrance site of the biopsy needle.

A two-view mammogram is performed with the first image obtained in the same position as the biopsy is performed.

Clip migration will be measured on the post-biopsy mammogram compared to the pre-biopsy mammography exam. Clip migration will be measured by the location of the clip with respect to the biopsy site on the immediate post-clip mammography images. While delayed clip migration has been found in case reports, the number of cases of this phenomenon is not felt to warrant additional mammography exams for this study.⁸ The millimeters of clip migration will be measured on the CC view and on the true lateral (ML or LM) views. Although migration usually only occurs in one plane, both planes will be reviewed and if there is migration in two planes, one component factor (Pythagorean Theorem as has been used on prior studies¹) will be calculated.

We will consider significant migration is anything greater than 10 mm from the biopsy site. The use of 10 mm has been documented on prior studies and will be considered as a differentiation point in this study between significant and nonsignificant movement. A further reason for the use of the 10 mm cut off is that at this institution, Savi Scout devices are commonly used for localization. This device is 12 mm long and can accurately be placed at a location bridging the biopsy site and biopsy clip. Any complications will be reported.

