13.2 Statistical analysis plan

The primary objective of the number and percentage of breast biopsy patients whose clip has greater than 10 mm from the biopsy site as significant clip migration will be estimated and two-sided 95% confidence interval will be calculated using the method of Clopper–Pearson interval for each arm separately. Fisher exact test will be used to examine if there is significant association between arms in proportion of significant clip migration. The average of distance of clip migration will be estimated with two-sided 95% CI for each arm separately using normal approximation. Two-group student t-test will be used to evaluate the mean difference in the distance of migration from the original biopsy site between arms.

Correlation between migration and breast densities (entirely fatty, scattered fibroglandular densities, heterogeneously dense, extremely dense), different approaches (lateral, medial, superior) to biopsy, if thinner or thicker breasts and age under procedure of retracted (arm2) vs nonretracted (arm1) will be evaluated in two ways for the secondary objectives. First, we will consider significant clip migration (yes, no) as binary outcome. Analysis of Variance method (ANOVA) will be used to compare age differences with controlling of procedures, and Cochran -Mantel-Haenszel Test will be

used to compare differences in categorical variables, e.g. breast density stratified by retracted (arm2) vs nonretracted (arm1). Logistic regression analysis will be explored to identify significant factors associated with clip migration. Odds ratio and two-sided 95% CI will be presented for each factor significantly contributed in the model. Second, we will consider distance of clip migration (mm) as continuous outcome. ANOVA will be used to evaluate the strength of association (beta coefficient in the regression model) and identify significant of factors associated with the distances of migration.

All analysis will be carried out with Statistical software SAS v9.4.

REFERENCES

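### The approach comparison in objective 3.2.2 is observational and adjusts for neither operator nor target location, so either could be reported as an effect of approach

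*Combined protocol and SAP*

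**What the plan says.** Section 6 leaves the biopsy approach to the radiologist on two grounds, one belonging to the operator and one to the patient: "The choice of positioning is decided on by the radiologist based on experience and best pathway to obtain to target". The choice precedes the procedure ("position determined by the radiologist ahead of time").

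Section 3.2.2 makes approach a study question: "Compare different approaches (lateral, medial, superior) to biopsy and evaluate if they have an impact on clip migration in both groups".

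Section 13.2 assigns the Cochran-Mantel-Haenszel test to categorical factors, of which approach is one. The test is to be "used to compare differences in categorical variables, e.g. breast density stratified by retracted (arm2) vs nonretracted (arm1"). The factors named for the secondary analyses are breast density, approach, breast thickness and age, alongside arm. The logistic regression is exploratory and has no fixed list of terms. Neither the performing radiologist nor the location of the target is named as a data item, stratum or covariate. Section 12.1 describes allocation only as 1:1, with 125 per arm.

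The number of operators is not given. Section 6 speaks of one attending at each procedure ("The attending radiologist then is notified and joins the technologist and patient in the biopsy suite"). Section 5.2 has a wider list of roles, but for screening: "The study coordinator, PI, or participating attending radiologist will screen potentially eligible patients".

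**The concern.** Patients who receive different approaches differ in at least two ways that the plan does not take into account: who did the biopsy, and where in the breast the target lay.

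Operator has routes to migration other than approach. The retraction is a manual step. The attending may also depart from the standard clip ("unless the attending radiologist determines another clip would be needed"). If the operators who favour one approach also have more migration for such reasons, their excess is credited to the approach.

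Target location raises the same problem more directly, since the best path to the target is a stated reason for the choice. If location also influences migration, its effect is mixed with that of approach however many radiologists take part.

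At stake is the reading of one secondary objective. A reader could conclude that an approach should be preferred or avoided because of migration when the difference came from the operator or the site of the lesion.

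**Working it through.** **The plan's own figures.** The documents give no figure for the approach comparison. The nearest stated figures are the powers in Table 1. Exact one-sided Fisher power at 125 per arm and 5% gives 99.96% for 50% v 20% (stated 99.9%) and 93.5% for 50% v 30% (stated 93.1%). The other six rows also agree closely. None of them depends on operator, location or approach.

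**Assumptions for the illustration (none is in the documents).** Two equally busy operators have migration risks r1 and r2, averaged over arms. There are two approaches, A and B. Operator 1 uses A in a proportion q of cases and operator 2 in 1 − q. Approach has no true effect.

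**Formulas.**
- Observed risk under A = q·r1 + (1 − q)·r2
- Observed risk under B = (1 − q)·r1 + q·r2
- Spurious difference = (2q − 1)(r1 − r2)

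**Results.**

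| Use of A | Operator risks | Risk under A | Risk under B | Difference (points) | Odds ratio |
|---|---|---|---|---|---|
| 60/40 | 40% v 30% | 36% | 34% | 2 | 1.09 |
| 60/40 | 50% v 25% | 40% | 35% | 5 | 1.24 |
| 70/30 | 45% v 25% | 39% | 31% | 8 | 1.42 |
| 70/30 | 50% v 25% | 42.5% | 32.5% | 10 | 1.54 |
| 80/20 | 50% v 25% | 45% | 30% | 15 | 1.91 |
| 80/20 | 50% v 20% | 44% | 26% | 18 | 2.24 |

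Worked example for the fifth row: 0.8 × 0.50 + 0.2 × 0.25 = 0.45 and 0.2 × 0.50 + 0.8 × 0.25 = 0.30, so the odds ratio is (0.45/0.55)/(0.30/0.70) = 1.91.

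**How often this would look like a finding.** With 125 patients per approach and a two-sided Fisher test at 5%, the rejection rate is 3.8% without confounding. It is 4.9% in the first row, 23% in the third and 82% in the last. The planned test is Cochran-Mantel-Haenszel over three approaches, so these rates are indicative only.

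**When the bias vanishes.** If q = 0.5 or r1 = r2, the difference (2q − 1)(r1 − r2) is zero.

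**Why stratifying by arm does not help.** Random allocation makes arm independent of operator, so in expectation each arm has the same operator mix within each approach. The spurious contrast therefore reappears inside each arm stratum.

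**Why stratifying by operator does.** Within operator 1 both approaches have risk r1, and within operator 2 both have r2. The odds ratio within each is 1.

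The same algebra applies to target location if two locations replace the two operators. The documents give no figure for how strongly location determines approach or migration.

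**The case against.** The strongest objection is that the documents do not establish the premise. A reader might infer that several radiologists operate, but no section says so. The phrase listing the PI or a participating attending concerns interview, screening, consent and data entry. More than one operator is still the natural reading: in section 6 the attending in the biopsy suite takes the biopsy consent, the radiologist then discusses the study, and study consent may be taken by the PI or a participating attending. That remains an inference, and the point about target location does not need it.

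A reader might also infer that 3.2.2 is confounded outright. That would require operators, or locations, to differ in both approach use and migration risk. The documents show neither, so the supportable statement is that the comparison is open to confounding.

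It is fair to add that 3.2.2 is one of four secondary objectives and that the exploratory logistic model does not exclude an operator term. Both points limit the scope. They do not meet the concern, because the plan does not say that operator or location will be recorded, and the test it specifies for categorical factors stratifies by arm alone.

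**Conclusion.** The point holds as a limited one. Followed as written, the plan would report an unadjusted comparison of non-randomised approaches, open to confounding by target location and, if more than one radiologist operates, by operator. The size cannot be derived from the documents. The illustrative odds ratios run from 1.09 to 2.24, the upper values need operator gaps of 25 to 30 points, and no bias arises if either difference is absent.

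Two further inferences are not supported. The first is that the comparison of retraction with no retraction is biased. Retraction is randomised, so operator, location and approach are balanced between arms in expectation, and chance imbalance is already covered by the type I error of the test. The second is that randomisation should be stratified by radiologist to cure this problem. Randomisation assigns retraction and not approach, so stratifying it would leave the approach comparison exactly as it is.

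**What to change.** 1. Record the performing radiologist and the target location for every case, with location in a few categories set in advance. If enrolment is complete, recover both from procedure records and imaging where possible.
2. In section 13.2, add radiologist as a stratum, with arm, in the Cochran-Mantel-Haenszel test for approach. Pool low-volume operators by a rule set before the data are examined.
3. Add radiologist and target location as terms in the logistic and distance models used for 3.2.2, and keep them whether or not they reach significance.
4. Describe the approach result as an observational association, in the plan and in the report.

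The cost is two data fields and a few degrees of freedom. If location largely determines approach, the adjusted estimate will be imprecise. That would show how little the data can say about approach as such. The allocation scheme, the sample size and the primary analysis need no change for this point.
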